8.2.5 Smoking History

The current and/or previous use of tobacco use will be recorded prior to randomization, as well as the estimated number of pack-years based on the approximate consumption per year.

8.2.6 Relevant medical history/current medical conditions

Relevant medical history and current medical conditions includes data prior to signing of the informed consent and should be recorded in the Medical History eCRF. Whenever possible, diagnoses and not symptoms should be recorded.

Significant findings that are observed after the subject has signed the ICF and that meet the definition of an AE must be recorded in the AE eCRF.

8.2.7 Prior and concomitant medications

Concomitant medications and prior medications taken over the 6 months preceding study enrollment for reasons other than HS will be captured at the screening visit, and updated as necessary in the relevant eCRF. In addition, information on the concomitant use of analgesics should be recorded by the subject in the eDiary and reviewed by the investigator at the scheduled visits.

8.2.8 Determination of the tuberculosis status

Determination of the tuberculosis (TB) status should be done at Screening and should be performed as defined by local guidelines. The TB status must be determined by medical history, signs, symptoms, TB testing (QuantiFERON-TB Gold assay). Any significant findings should be recorded in the eCRF.

QuantiFERON TB-Gold In-Tube assay

A QuantiFERON® TB-Gold In-Tube assay (QFT) to screen a population for latent tuberculosis infection ([Doherty et al 2008](#)) will be used at Screening to evaluate the subjects' eligibility for the study. This blood-based assay is specific for *Mycobacterium tuberculosis* and is not influenced by previous *Bacillus Calmette-Guérin* vaccination or by exposure to other *Mycobacteria* species. Furthermore, this test, in contrast to the purified protein derivative (PPD) skin test, is also insensitive to a booster effect since the subject is not exposed to the vaccine. The assay measures the production of interferon-gamma and presents it relative to a negative and a positive control sample ([Manuel and Kumar 2008](#)). The QuantiFERON®-TB Gold assay test will be supplied by the central laboratory. Details on the collection, shipment of samples and reporting of results by the central laboratory are provided to investigators in the study-specific Laboratory Manual.

The workflow of sample handling in case of positive or indeterminate test results is provided in [Figure 8-1](#).

- If the test result is **negative**, the subject may be randomized.
- If the test result is **positive**, the investigator should perform a work-up for the test result as per local procedures. If a TB work-up was conducted prior to the screening of the subject, results of the work-up can be used to assess eligibility if the work-up was conducted within 12 weeks prior to randomization.
 - Subjects **positive** for latent TB per work-up may be randomized to the trial if sufficient treatment has been initiated according to local routine clinical practice and completed at least four weeks before randomization.
 - Subjects positive for active TB per work-up are not eligible for the study.
 - Subjects negative for TB (no signs of latent or active TB) per work-up may be randomized to the trial.
- If the test result is **indeterminate**, the investigator **may repeat the test once or may proceed directly to perform the work-up** for the test result as per local procedures. This action is at the discretion of the investigator. If a TB work-up was conducted prior to the screening of the subject, results of the work-up can be used to assess eligibility if the work-up was conducted within 12 weeks prior to randomization.
 - If the second test is negative, the subject may be randomized.
 - If the second test is positive, the investigator should perform work-up as per local guidelines. Subjects positive for **latent** TB per work-up may be randomized to the trial if sufficient treatment has been initiated according to local routine clinical practice and completed at least four weeks before randomization. Subjects **positive** for **active** TB per work-up **are not eligible** for the study. Subjects negative for TB (no signs of latent or active TB) per work-up may be randomized to the trial.
 - If the second test is again indeterminate, the investigator should perform follow-up for the test result as per local procedures. Subjects tested positive for **latent** TB per work-up may be randomized to the trial if sufficient treatment has been initiated according to local routine clinical practice. Subjects positive for **active** TB per work-up are not eligible for the study. Subjects negative for TB per work-up (no signs of latent or active TB) may be randomized to the trial if the work-up was conducted 12 weeks prior to randomization.

If eligibility is being assessed with only 1 test result and a TB work-up (i.e., no second TB test will be performed), the TB test to assess eligibility must have been done via the central laboratory for the study within the Screening Epoch (within 4 weeks prior to randomization) and TB work-up will only be considered if it was completed **within 12 weeks** prior to randomization. Subjects positive for latent TB per work-up may be randomized to the trial if sufficient treatment has been initiated according to local routine clinical practice and completed at least four weeks before randomization. Subjects positive for active TB per work-up are not eligible for the study. Subjects negative for TB per work-up (no signs of latent or active TB) may be randomized to the trial.

[figure not shown]
[figure not shown]

Figure 8-1 Tuberculosis screening flowchart

The subject will not be eligible for randomization if "active tuberculosis is present" or if "latent tuberculosis is present and is untreated as per local guidelines". * If the first QuantiFERON® TB-Gold In-Tube assay (QFT) is indeterminate, the investigator may choose to perform a second QFT or refer the subject for tuberculosis workup per local guidelines. ** If the result of QFT is "positive" or the results of 2 sequential QFTs are "indeterminate", the subject must be referred to have a tuberculosis workup per local guidelines (if no workup within 12 weeks prior to randomization is available).

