
• To explore the efficacy of secukinumab compared to placebo with respect to HiSCR response after 16 weeks of treatment and the sustained efficacy over time in bio-naïve patients.• To explore the efficacy of secukinumab compared to placebo with respect to HiSCR response after 16 weeks of treatment and the sustained efficacy over time in patients with body weight lower and higher than 90 kg (<90 kg and ≥90 kg).	
• Achievement of HiSCR at Week 16 and up to Week 52 in bio-naïve patients.• Achievement of HiSCR at Week 16 and up to Week 52 in patients with body weight lower and higher than 90 kg (<90kg and ≥90kg).

3 Study design

This is a multicenter, randomized, double-blind, placebo controlled, parallel group study with two secukinumab dose regimens in approximately 541 patients with moderate to severe HS.

The study consists of: Screening (up to 4 weeks), Treatment Period 1 (16 weeks) and Treatment Period 2 (36 weeks). Subjects who prematurely discontinue the study, or who complete the study and cannot or do not wish to continue in a planned optional extension study, will need to complete a post-treatment Follow-Up period (8 weeks).

Safety, efficacy, biomarker and pharmacokinetic measurements of secukinumab will be assessed.

An outline of the study design is presented in [Figure 3-1](#), and a detailed visit and assessment schedule is provided in [Table 8-1](#).

Screening (Screening to Randomization)

A screening period of up to 4 weeks will be used to assess the subject's eligibility and to washout and/or taper prohibited medication(s). Two screening visits will be performed: Visit 1 (Day -28 to Day -14) and Visit 2 (Day -13 to Day -1). Subjects can be re-screened if the subject screen fails due to a transient medical condition or due to an insufficient prohibited medication washout period. Subjects can be re-screened only once and no study-related re-screening procedure should be performed prior to re-consenting the subject.

Important note:

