5.2 Exclusion criteria

Patients meeting any of the following criteria are not eligible for inclusion in this study.

1. Total fistulae count ≥ 20 at baseline.
2. Any other active skin disease or condition that may interfere with assessment of HS.
3. Active ongoing inflammatory diseases other than HS that require treatment with prohibited medications (see [Table 6-2](#)).
4. Underlying conditions (including, but not limited to metabolic, hematologic, renal, hepatic, pulmonary, neurologic, endocrine, cardiac, infectious or gastrointestinal such as inflammatory bowel disease) which in the opinion of the investigator significantly immunocompromises the patient and/or places the patient at unacceptable risk for receiving an immunomodulatory therapy.
5. Current severe progressive or uncontrolled diseases which renders the patient unsuitable for the trial or puts the patient at increased risk, including any medical or psychiatric condition which, in the Investigator's opinion, would preclude the participant from adhering to the protocol or completing the study per protocol.
6. Use or planned use of prohibited treatment. Washout periods detailed in the protocol have to be adhered to (see [Table 6-2](#)).
7. For patients enrolling in the non-antibiotic strata: use of systemic antibiotics for the treatment of HS within 28 days before baseline.
For patients enrolling in the antibiotic strata: patients enter the study under concomitant treatment with systemic antibiotics (as per protocol) on a stable dose (defined as a dose or dose regimen that has not changed in the previous 28 days before baseline and is considered unlikely to change at least for the first 16 weeks during the study).
8. History of hypersensitivity to any of the study drug constituents.
9. Previous exposure to secukinumab (AIN457) or any other biologic drug directly targeting IL-17 A/F or the IL-17 receptor.
10. History of chronic or recurrent systemic infections or active systemic infections during the last two weeks (exception: common cold) prior to randomization.
11. Evidence of tuberculosis infection as defined by a positive QuantiFERON® TB-Gold test (QFT) at screening. Patients with a positive or indeterminate QFT test may participate in the study if a full tuberculosis work-up (according to local practice/guidelines) completed within 12 weeks prior to randomization, establishes conclusively that the patient has no

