evidence of active tuberculosis. Subjects positive for latent TB per work-up may be randomized to the trial if sufficient treatment has been initiated according to local routine clinical practice and was completed at least four weeks before randomization.

12. Medical history record of infection with human immunodeficiency virus (HIV), hepatitis B or C prior to randomization, except for hepatitis C successfully treated and cured.
13. History of lymphoproliferative disease or any known malignancy or history of malignancy of any organ system treated or untreated within the past 5 years, regardless of whether there is evidence of local recurrence or metastases (except for skin Bowen's disease, or basal cell carcinoma or actinic keratoses that have been treated with no evidence of recurrence in the past 12 weeks; carcinoma in situ of the cervix or non-invasive malignant colon polyps that have been removed).
14. History or evidence of ongoing alcohol or drug abuse, which in the opinion of the investigator will prevent the patient from adhering to the protocol and completing the study.
15. Pregnant or lactating women.

16. Women of childbearing potential, defined as all women physiologically capable of becoming pregnant, unless they are using methods of contraception during the entire study or longer if required by locally approved prescribing information (e.g. in European Union (EU) 20 weeks).

Contraception methods include:

- Total abstinence, when this is in line with the preferred and usual lifestyle of the patient. Periodic abstinence (e.g. calendar, ovulation, symptothermal, post-ovulation methods) and withdrawal are not acceptable methods of contraception.
- Female sterilization (have had surgical bilateral oophorectomy with or without hysterectomy), total hysterectomy or bilateral tubal ligation at least six weeks before taking study treatment. In case of oophorectomy alone, only when the reproductive status of the woman has been confirmed by follow-up hormone level assessment.
- Male sterilization (at least 6 months prior to screening). The vasectomized male partner should be the sole partner for that patient.
- Barrier methods of contraception: Condom or Occlusive cap (diaphragm or cervical/vault caps). For United Kingdom: with spermicidal foam/gel/film/cream/vaginal suppository.

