6.3.2 Treatment assignment, randomization

The investigator or his/her delegate will contact the IRT after confirming that the subject fulfills all the inclusion/exclusion criteria. The IRT will assign a randomization number to the subject, which will be used to link the subject to a treatment arm and will specify a unique medication number for the package of study drug to be dispensed to the subject. The randomization number will not be communicated to the investigator or his/her delegate.

The randomization numbers will be generated using the following procedure to ensure that treatment assignment is unbiased and concealed from subjects and investigator staff. A patient randomization list will be produced by the IRT provider using a validated system that automates the random assignment of patient numbers to randomization numbers. These randomization numbers are linked to the different treatment arms, which in turn are linked to medication numbers. A separate medication list will be produced by or under the responsibility of Novartis Clinical Drug Supply using a validated system that automates the random assignment of medication numbers to packs containing the investigational drug(s).

Randomization will be stratified by region, concomitant antibiotic use (Yes/No) and body weight (weight < 90kg / ≥ 90kg).

The randomization scheme for subjects will be reviewed and approved by a member of the Randomization Group.

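### After two indeterminate TB tests, Protocol 8.2.8 lets a patient with latent TB be randomised once treatment has started, whereas exclusion 11 requires it to have been completed four weeks earlier

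*Protocol*

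**What the plan says.** Exclusion criterion 11 (Protocol 5.2) is the formal rule. Its scope includes indeterminate results: "Patients with a positive or indeterminate QFT test may participate in the study if a full tuberculosis work-up" rules out active disease. For latent TB found on work-up, it requires that sufficient treatment was started and "was completed at least four weeks before randomization". It makes no exception for a patient with two indeterminate tests.

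Protocol 8.2.8 turns this into a sequence of branches. In three places it gives the full condition, that treatment "has been initiated according to local routine clinical practice and completed at least four weeks before randomization": when the first test is positive, when an indeterminate first test is followed by a positive second one, and when eligibility rests on one test plus a work-up.

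The branch for a second indeterminate result differs. There a patient with latent TB on work-up "may be randomized to the trial if sufficient treatment has been initiated according to local routine clinical practice", with nothing about completion or a four-week interval.

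The note under Figure 8-1 bars randomisation if active TB is present or if "latent tuberculosis is present and is untreated as per local guidelines".

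**The concern.** The protocol states a safety eligibility rule in two ways for the same patient. A site working through 8.2.8 step by step reaches a permissive sentence in the two-indeterminate branch. A site checking exclusion 11 reaches a bar.

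The patient concerned has latent TB and has not finished treatment, or finished it less than four weeks ago, and would start an immunomodulator for which the protocol lists infections among the observed risks (Section 4.5). If a site acts on the branch alone, the result is an eligibility breach that the protocol's own text invited.

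Nothing in the protocol explains why latent TB should be handled more leniently after two indeterminate tests than after one. In both cases it is the work-up that establishes latent TB.

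**Working it through.** There is no planned figure to reproduce. The check is a comparison of the texts, plus one piece of arithmetic on dates.

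**Step 1. The statements side by side**

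| Place in the protocol | Test history | Condition on latent-TB treatment |
|---|---|---|
| 5.2, exclusion 11 | QFT positive or indeterminate | Started, and completed at least 4 weeks before randomisation |
| 8.2.8 | First test positive | Started, and completed at least 4 weeks before |
| 8.2.8 | First indeterminate, second positive | Started, and completed at least 4 weeks before |
| 8.2.8 | One test plus work-up | Started, and completed at least 4 weeks before |
| 8.2.8 | First and second indeterminate | Started only |

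Four statements require completion and one does not.

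**Step 2. Does nearby text supply the missing condition?** The Figure 8-1 note excludes latent TB that is untreated by local guidelines. A patient part-way through a course is arguably not untreated, so the note does not restore the requirement. The flowchart itself is not reproduced in the text available for review, so nothing here rests on it.

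**Step 3. Who gets different answers?**

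- Treatment completed at least 4 weeks before randomisation: eligible on this point under both texts.
- Treatment not started: not eligible under either text.
- Treatment under way, or completed less than 4 weeks before: barred by exclusion 11, admitted by the branch.

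**Step 4. Can a patient in this branch start treatment during screening and still meet exclusion 11?**

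Inputs:

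- Protocol Section 3: "A screening period of up to 4 weeks will be used to assess" eligibility, with Screening Visit 1 on Day -28 to Day -14 and Visit 2 on Day -13 to Day -1.
- SAP 2.1.1: there is no Day 0, and a date before Day 1 is numbered as that date minus Day 1. Day -28 is therefore exactly 28 days before Day 1.
- Exclusion 11: completion at least 4 weeks before randomisation, and 4 × 7 = 28 days.

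Take randomisation and first dose to fall on Day 1. Then:

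- the first screening QFT is at most 28 days before randomisation;
- the second QFT is done later, so it falls fewer than 28 days before;
- treatment begun because of the second result starts fewer than 28 days before;
- completion cannot precede the start, so it is also fewer than 28 days before.

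The requirement of at least 28 days cannot be met in that screening episode. For every such patient exclusion 11 says no, while the branch says yes as soon as treatment has started.

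**The case against.** The strongest reply is that exclusion 11 governs. A patient who meets any exclusion criterion is ineligible, and Section 6.3.2 allows the site to contact the randomisation system only "after confirming that the subject fulfills all the inclusion/exclusion criteria". Section 8.2.8 is an assessment procedure written in permissive terms, and nothing says it overrides 5.2. Read together, the answer is fixed: not eligible. Monitoring also verifies adherence to the eligibility criteria in full (Section 11.3). With four statements against one, the intent is plain and this looks like a dropped phrase.

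Most of that stands. It lowers the chance of a wrong randomisation and argues against treating this as a grave defect. It does not make the text consistent, and it relies on the site noticing that the detailed procedure is incomplete. Monitoring would find a breach but might not prevent one.

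It can also be said that the date arithmetic applies equally to the second-positive branch. That is true, but there the text states the completion rule, so the site gets one answer.

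Finally, the Figure 8-1 note says only who is ineligible. It does not say that every treated patient is eligible, so it does not itself contradict exclusion 11. That is fair, and aligning it is secondary.

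**Conclusion.** The concern holds. The second-indeterminate branch of 8.2.8 is wrong as written and should be corrected.

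The breach is confined to patients with two indeterminate QFTs and latent TB on work-up whose treatment is unfinished or ended fewer than 28 days before randomisation. The documents give no count, and the group is likely to be small because several conditions must coincide. Within it, the conflict is certain for anyone starting treatment after the second result in the same screening episode, given the 28-day screening limit and randomisation on Day 1. A later re-screening, after treatment has been completed, is a separate case.

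The issue is one of patient safety and protocol consistency and has no bearing on the statistical analysis.

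**What to change.** In the second-indeterminate branch of Protocol 8.2.8, extend the latent-TB sentence to require completion at least four weeks before randomisation, matching exclusion 11 and the other three branches.

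Two small edits can be made at the same time:

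- Align the Figure 8-1 note, so that it bars latent TB whose treatment was not completed at least four weeks before randomisation.
- In the same branch, the sentence for patients negative on work-up says they "may be randomized to the trial if the work-up was conducted 12 weeks prior to randomization". Insert *within* before the 12 weeks, as exclusion 11, the parent bullet and the figure note already have it. This is wording only.

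The cost is a few words. No new procedure or data are needed, because exclusion 11 already sets the rule.

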8.3 Efficacy

Whenever possible, efficacy assessments for an individual subject should be performed by the same member of the study site staff throughout the study.

In the event of a pandemic/epidemic that limits or prevents on-site study visits, selected efficacy assessments (excluding lesion count) can alternatively be done via phone calls, virtual contacts or visits of site staff to the subject's home, depending on local regulations and capabilities.

Efficacy assessments based on Patient Reported Outcomes (PROs) might alternatively be done remotely from the subject's home (e.g. online or by telephone interview), depending on local regulations and technical capabilities.

8.3.1 Hidradenitis Suppurativa Clinical Response (HiSCR)

The HiSCR ([Kimball et al 2014](#)) is defined by the status of three types of lesions: abscesses (fluctuant, with or without drainage, tender or painful), inflammatory nodules (tender, erythematous, pyogenic granuloma lesion), and draining fistulas (sinus tracts, with communications to skin surface, draining purulent fluid). The definition of responders to treatment (HiSCR achievers) is:

- at least a 50% reduction in abscesses and inflammatory nodules (ANs),
- no increase in the number of abscesses, and
- no increase in the number of draining fistulas from baseline.

The HiSCR will be derived from the individual lesion counts of abscesses, nodules and fistulae at scheduled visits as indicated in the assessments schedule and as such will not be recorded in the eCRF.

Individual lesion count

The HS affected areas e.g. right and left axillary (armpit), right and left gluteal ("buttock"), right and left inguinal-femoral (groin), perineal, pubic, sternal, right and left sub-mammary (breast) and others will be assessed by the physician for abscesses, inflammatory nodules, draining fistulas, total fistulae, and other lesions.

Whenever possible, the same physician should perform the lesion count throughout the study.

Inflammatory lesions, including abscesses, nodules, draining fistulae, total fistulae and other lesions will be counted by area.

Individual lesion counts will be performed for all lesions as outlined in the [Table 8-1](#). The lesion count will include any existing and newly observed lesions and will be recorded in the eCRF. The HS lesions are defined as ([Lipsker et al 2016](#); [Zouboulis et al 2017](#)):

- *Inflammatory nodules (N)* that are typically raised, deep-seated, three-dimensional, round, tender, erythematous, infiltrated and possibly pyogenic granuloma lesions with a diameter of >10 mm
- *Abscesses (A)* that are often inflammatory, painful, tender but fluctuating mass with a diameter of >10 mm, surrounded by an erythematous area; the middle of an abscess contains pus

- *Draining fistulae* (DF); sinus tracts, raised, tender but fluctuating longitudinal mass of variable length and depth, with communications to skin surface, draining purulent fluid
- *Fistulae* (F): total fistulae defined as sinus tracts, raised, tender but fluctuating longitudinal mass of variable length and depth, with communications to skin surface, both draining and non-draining purulent fluid.

8.3.2 Patient's Global Assessment of Skin Pain - NRS in the past 24 hours

The Patient's Global Assessment of Skin Pain - Numerical Rating Scale (NRS) in the past 24 hours will be used to assess pain "at its worst" and the average skin pain due to HS in the last 24 hours. The NRS is a segmented numeric version of the visual analog scale (VAS) in which a respondent selects a whole number (0–10 integers) that best reflects the intensity of their pain ranging from 0 (no skin pain) to 10 (skin pain as bad as you can imagine). Skin Pain will be collected as specified in the assessment schedule. To assess this, the patient should concentrate on the pain that his/her skin lesions generate. The Patient's Global Assessment of Skin Pain - NRS will be completed by the subject using the eDiary device.

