12.4.2 Statistical model, hypothesis, and method of analysis

The statistical hypotheses for the primary endpoint being tested is that there is no difference in the proportion of HiSCR at Week 16 in any of the secukinumab regimens versus placebo regimen.

Let p_j denote the proportion of HiSCR at Week 16 for treatment regimens j , $j = 0, 1, 2$ where

- 0 corresponds to placebo regimen,
- 1 corresponds to secukinumab 300 mg q2w s.c.,
- 2 corresponds to secukinumab 300 mg q4w s.c.,

In statistical terms, $H_j: p_j = p_0, H_{A_j}: p_j \neq p_0$ for the j th secukinumab regimen, i.e.

H_1 : secukinumab 300 mg q2w s.c. is not different to placebo regimen with respect to HiSCR after 16 weeks of treatment.

H_2 : secukinumab 300 mg q4w s.c. is not different to placebo regimen with respect to HiSCR after 16 weeks of treatment.

The primary analysis method will be logistic regression with treatment group, geographical region, Hurley stage, use of antibiotic, baseline body weight and baseline AN counts as explanatory variables. Odds ratios will be computed for comparisons of secukinumab dose regimens versus placebo utilizing the logistic regression model fitted. In case of response rates of 0% or of 100% in one of the treatment groups, Fisher's exact test will be applied. Risk difference and confidence intervals for risk difference will be provided.

The detailed testing strategy including the primary endpoint analysis is provided in [Section 12.5](#). Efficacy of two secukinumab regimens compared to placebo with respect to HiSCR after 16 weeks of treatment could be demonstrated if H_1 and/or H_2 is/are rejected and the treatment effect is in favor of secukinumab.

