**Continuous variables:**

- Baseline AN count
- Baseline inflammatory nodule count
- Baseline abscess count
- Baseline draining fistula count
- Baseline total fistulae count
- Baseline NRS
- Baseline Hidradenitis Suppurativa Physician's Global Assessment (HS-PGA)
- Baseline modified Hidradenitis Suppurativa Score (mHSS)
- Baseline hsCRPBsl ESR

- Dermatology Life Quality Index (DLQI) total score
- EuroQol-5 Dimension (EQ5D)
- Time since diagnosis of HS
- Time since HS symptom(s) onset

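### Among lesion counts, the primary HiSCR model adjusts only for the AN total, although response is also judged against baseline abscess and draining-fistula counts; adding both would be a small gain at almost no cost

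*Protocol*

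**What the plan says.** Protocol 8.3.1 sets three conditions for HiSCR: a fall of at least half in the AN count, no rise in abscesses, and "no increase in the number of draining fistulas from baseline". Protocol 12.4.1 defines baseline as the last assessment up to the day of first dosing.

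Protocol 12.4.2 specifies "logistic regression with treatment group, geographical region, Hurley stage, use of antibiotic, baseline body weight and baseline AN counts as explanatory variables". Among lesion counts, only the AN total (abscesses plus inflammatory nodules) is there.

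The other two counts are available. Protocol 8.3.1 states "Inflammatory lesions, including abscesses, nodules, draining fistulae, total fistulae and other lesions will be counted by area", Table 8-1 schedules the count at baseline, and SAP 2.4 tabulates "Baseline abscess count" and "Baseline draining fistula count". Neither appears as a covariate in the sensitivity and supportive analyses of Protocol 12.4.4 or in the repeated-measures HiSCR model of SAP 2.13 and 5.4.2.2. No reason is given.

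The supplied SAP covers the final Week 52 analysis. Its Introduction places the primary and secondary analyses in a separate Week 16 SAP, which was not supplied.

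**The concern.** Two patients with the same AN total can face different hurdles. With no abscesses at baseline, one abscess at Week 16 means non-response; with three at baseline, up to three are allowed. The AN total cannot separate 0 abscesses plus 8 nodules from 4 plus 4, and a three-level Hurley stage is not a draining-fistula count.

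The choice also departs from the protocol's own pattern. NRS30 is adjusted for baseline NRS (12.5.1), HS-PGA and DLQI response for their own baselines (12.6), and flare, which depends only on AN, for baseline AN (12.5.1). HiSCR has three baseline-referenced parts and is adjusted for one. Randomization is stratified by region, antibiotic use and weight (6.3.2), so nothing else in the design balances the two counts.

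What is at stake is some efficiency in the primary comparison, chiefly for q4w, which has the smaller alpha.

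**Working it through.** **1. The plan's own power.** Inputs: 30% v 50% (Protocol 12.8.1); two-sided alpha of 4% (q2w) and 1% (q4w), and 471 patients at 1:1:0.5:0.5 (12.8). With placebo pooled, n = 471/3 = 157 per arm.

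Power = Φ{[d√n − z√(2 × 0.40 × 0.60)] / √(0.30 × 0.70 + 0.50 × 0.50)}, with d = 0.20.

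- Uncorrected: 94.5% (4%) and 85.6% (1%).
- Continuity-corrected: replace n by n(1 − 1/(nd))² = 157 × (1 − 1/31.4)² = 147.2. Power is 93.0% and 82.8%.

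The corrected figures match the stated 93% and 83%. No covariate enters them.

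**2. How far the baseline count moves the hurdle.** This is an illustration with an assumed mean of 1.5 abscesses. If every patient had the same stable Poisson rate, P(no increase) at baseline b would be P(X ≤ b). If rates vary between patients (gamma, shape k, mean 1.5), the later count given b is negative binomial with size k + b and p = (k/1.5 + 1)/(k/1.5 + 2). For k = 1, p = 0.625, so b = 0 gives 0.625 = 63% and b = 1 gives 0.625² × (1 + 2 × 0.375) = 68%.

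| Assumption | b=0 | b=1 | b=2 | b=3 |
|---|---|---|---|---|
| Same rate for all | 22% | 56% | 81% | 93% |
| Gamma, k=2 | 49% | 65% | 75% | 81% |
| Gamma, k=1 | 63% | 68% | 73% | 76% |
| Gamma, k=0.5 | 76% | 71% | 71% | 72% |

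The steep gradient depends on the equal-rate assumption.

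**3. Simulated gain on the risk difference.** Two sets used 180 v 180 patients, and all three had AN count and a Hurley-type stage already in the model. The figure is the variance ratio of the risk difference after adding log(1+count) for both lesion types.

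- Assumed lesion rates, HiSCR about 35% v 58%, three scenarios of 800 trials: 0.970, 0.954, 0.984 (linear terms 0.983, 0.976, 0.989).
- Gamma-Poisson rates varying between patients, four scenarios of 1,200 trials: 1.016, 0.986, 0.994, 0.970. The 1.016 is within simulation noise.
- Five further scenarios with varying patient rates: 0.97-1.00, mean treatment z slightly higher in all five, power change at 1% alpha from −0.3 to +1.6 points.

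**4. Conversion to power.** Replace n by n/(1 − R²), where R² is the share of remaining outcome variance explained (uncorrected formula).

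| R² | N=471, 4% / 1% | N=541, 4% / 1% |
|---|---|---|
| 0 | 94.5 / 85.6 | 96.9 / 90.8 |
| 0.02 | 94.9 / 86.5 | 97.1 / 91.5 |
| 0.05 | 95.5 / 87.7 | 97.5 / 92.4 |

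At R² = 0.05 the gain is about 1.0 and 2.1 points with 471 patients, and about 0.7 and 1.6 points with 541.

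**5. Odds-ratio scale.** Simulation of 3,000 trials per setting, 157 per arm, 30% v 50%, with one standardised composite of the omitted counts, assumed independent of AN:

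| OR per SD of composite | Power at 4%, without → with | Power at 1%, without → with |
|---|---|---|
| 1.00 | 94.8 → 94.7 | 86.2 → 86.2 |
| 1.49 | 94.7 → 95.2 | 86.1 → 87.5 |
| 2.23 | 94.7 → 96.7 | 85.4 → 90.2 |

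At OR 1.49 the treatment log odds ratio moves from 0.872 to 0.908 while its SE rises from 0.2408 to 0.2468, so the ratio goes from 3.62 to 3.68. The SD of the risk difference falls from 0.0534 to 0.0524, a variance ratio of (0.0524/0.0534)² = 0.963, inside the range of step 3. At OR 2.23 the ratio is (0.0510/0.0540)² = 0.892, beyond anything the lesion-count simulations produced. The nearly 5-point gain in that row is therefore not taken as realistic.

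**The case against.** The strongest reply is that this is a preference. A short prespecified covariate list is defensible, the test is valid as it stands, and a baseline value is not prognostic merely because it appears in the response definition. That is right as to validity: nothing in the documents is contradicted.

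The existing terms also carry part of the information. The AN total contains the abscesses, and Hurley stage partly tracks tract burden (Protocol 8.2.4). The Amendment 2 rationale cites inter-rater variability in assessing draining fistulae, and a noisily rated count is a weaker covariate. These points stand, and they help explain why the simulated gain is small.

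Three stronger readings are tempting, and the documents do not support them:

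- A reader might infer that precision is demonstrably being lost. No association of either count with HiSCR is given, so the gain rests on assumed lesion distributions and may be nil.
- A reader might take the 22% to 93% gradient as the size of the problem. It assumes one abscess rate for all patients; with varying rates it shrinks sharply and can vanish. It also ignores that a responder must already have the 50% AN fall.
- A reader might expect a tighter odds ratio. Its SE rises with adjustment; the benefit is power. Reduced variance applies to the risk difference, which 12.4.2 reports alongside the odds ratio.

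Finally, Protocol 12.4.3 imputes the underlying continuous variables, so the component counts may already enter the Week 16 imputation model. That cannot be checked here.

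**Conclusion.** The point holds as a minor improvement. HiSCR refers to three baseline lesion counts and the protocol's primary model uses one of them, in contrast to its other responder models. The omission does not bias the comparison, raise type I error or undermine the stated power.

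The plausible gain is about 0-3% of risk-difference variance, at most about 5%, equivalent to roughly 0-16 and at most about 27 of 541 patients (0.03 × 541; 0.05 × 541). In power it is about 0-2 points, largest for q4w at 1% alpha. These figures rest on assumed lesion rates, on a Hurley-type stage standing in for the real one, and on simulations without trial data. The conclusion also depends on the Week 16 SAP not already including the counts.

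**What to change.** Check the Week 16 SAP first. If the two counts are absent from its primary HiSCR model, add log(1 + baseline abscess count) and log(1 + baseline draining-fistula count), both from the randomization visit, to the model in Protocol 12.4.2, fixed before Week 16 unblinding.

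If unblinding has already taken place, leave the primary model alone and report the expanded model as a labelled sensitivity analysis.

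Leave the bio-naive and body-weight HiSCR models in Protocol 12.6 as they are. They have fewer patients and events, and none of the work above examines extra terms there.

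The cost is one line in the protocol and the Week 16 SAP and two more model terms. No new data are needed, and the endpoint, hypotheses and alpha split do not change.
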